The purpose of this study is to understand whether the couple therapy that is used in practice is effective in preventing situational couple violence. More specifically, we will focus on couples with mild to moderate forms of situational couple violence to investigate how couple therapy can be effective in preventing the escalation and recurrence of situational couple violence. For this purpose, the response of partners to therapy will be investigated by integrating self-report questionnaires and psycho-physiological markers of emotion. All couples who exhibit characteristics of characterological violence will be excluded from the study.

The change in partners' emotion regulation over the course of therapy will be measured using psycho-physiological markers of stress response. Using these measurements, the interplay between changes in violence and the emotion regulation of partners in relation to each other will be investigated in a dyadic (couple) context. More specifically, the following aims will be pursued to understand the relationship between couple therapy, emotion regulation, and violence:

Aim 1: Examine the associations between IPV and each partner's psychophysiological regulation in terms of Hypothalamic Pituitary Adrenal (HPA) activity and Parasympathetic Nervous System (PNS) activity. This aim will investigate whether dysregulation of HPA and PNS activity in each partner is correlated with the existence and intensity of IPV for the couple. Existence and intensity of IPV will be assessed using self and partner report questionnaires. HPA activity will be measured using salivary cortisol, and PNS activity will be measured using vagal tone and vagal regulation by using an eMotion Heart Rate Variability (HRV) sensor.

Aim 2: Examine the longitudinal effects of conjoint therapy on IPV and each partner's psychophysiological regulation in terms of HPA and PNS activity. This aim will investigate whether the reported intensity of IPV for couples decreases after couples start therapy and whether this change is correlated with regulation of HPA and PNS activity for each partner. This aim will examine the effect of couple therapy on each individual partner separately.

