Aim 3: Examine the longitudinal effects of partners' psychophysiological regulation on each other's psychophysiological regulation and on IPV. This aim will explore patterns of change in each partner's psychophysiological regulation as a function of their partner's psychophysiological regulation. More specifically, this aim will investigate whether couple therapy facilitates change by restructuring the relationship in such a way that the change in one partner's behavior helps the other partner regulate their emotions in a functional way.

Principal Investigator: [name]

Protocol Summary for IRB: Feasibility Study of Couple Therapy Treatment for Situational Couple Violence (IRB# 09-13-27)

Study Design

This study has a longitudinal design that requires therapy sessions over 8 weeks, with data collected at every visit. Couple therapy will be conducted using an attachment and affect regulation based therapy approach described below under “Couple Therapy”. Data will be collected in the form of self-report and partner-report measures, as well as physiological screening of the neuroendocrine system. These measures are described below under “Data Collection”. The flowchart for the design of the study is shown below.

After careful screening, eight couples will be enrolled in the study. The couples will be divided into two groups, each consisting of four couples. Distribution of participants to the two groups will be randomized. Group 1 will immediately begin 8 weeks of couple therapy and Group 2 will complete 8 weeks of couple therapy after an 8 week (+ or – 10 days) waiting period is completed.

The pre-test, post-test, and follow-up physiological data collection will be completed at the following times for couples beginning the 8 weeks of couple therapy:

- Baseline Pre-test: Before starting the therapy sessions.
- Post-test: One week (+ or – 5 days) after the end of the therapy session.
- Follow-up: Three months (+ or – 10 days) after the post-test.

The participants that are assigned to Group 2 will also complete the physiological data collection before starting the 8 week waiting period. When participating in the 8 week couple therapy Group, participants will complete a small number of assessments at each therapy session.

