The participants that are assigned to Group 2 will have one additional assessment session at baseline. In order to help those in Group 2 who will not be receiving therapy for the first 8 weeks, individuals in this group will be taught safety planning, given information on local resources to help victims of violence, and will be instructed in stress and anger management strategies. Following this 8 week waiting period, they will receive 8 weeks of couple therapy unless they choose not to. All the physiological and behavioral data collection will be repeated once Group 2 starts therapy.

If a couple discontinues after the baseline and before the end of the study (EOS), the EOS assessments should be obtained.

For couples in Group 1, involvement in the study will last throughout a period of five months with approximately 14 hours of active participation. For couples in Group 2, involvement in the study will last throughout a period of seven months with approximately 16 hours of active participation.

Couple Therapy

Each couple will receive couples therapy for 8 weekly sessions. Each therapy session will last approximately an hour. The therapy sessions will take place in UH Mood Disorders Program, room #12-126, on the 12th floor of the W.O. Walker Center. An attachment and affect regulation based therapy approach will be used in couple therapy.

Principal Investigator: [name]

Protocol Summary for IRB: Feasibility Study of Couple Therapy Treatment for Situational Couple Violence (IRB# 09-13-27)

The participants will receive standard couples therapy that they would have access to outside of the study. The therapy itself is not experimental, but rather it is the data collection, physical measures, and timing which are the experimental portions of the study.

All therapies will be conducted by the PI, [name]. [name] is a Licensed Marriage and Family Therapist and AAMFT (American Association of Marriage and Family Therapy) approved clinical supervisor.

Hypotheses

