Table 2. Assessment schedule

Principal Investigator: [name]

Protocol Summary for IRB: Feasibility Study of Couple Therapy Treatment for Situational Couple Violence (IRB# 09-13-27)

Efficacy & Data Analysis

Data analysis plan

This study is designed to be an initial feasibility study to collect pilot data in pursuit of the following aims:

Aim 1: After the first wave of data collection (pretest), the cross sectional relations among the basic constructs of interest will be examined. These basic constructs are psychophysiological markers of emotion regulation and IPV. In order to understand how these markers are related to violence, t-tests will be used to understand this effect. Each partner's HPA and PNS activity is expected to be directly linked to the violence perpetrated by their partner.

Aim 2: The objective of this aim is to understand whether violence decreases over time following therapy and whether this decrease is accompanied by respective change in physiological markers of emotion regulation. For this purpose, series of chi-square-test will be used as well as qualitative analysis.

Aim 3: In order to represent the interaction between the emotion regulation of partners, links from emotion regulation of each partner to the emotion regulation of the other partner at the next time point are included. Qualitative analysis with a grounded theory approach will be used.

The proposed sample size (8 couples) is chosen as a tradeoff between data collection time and statistical power. Since this is a feasibility study, we chose to start with a small sample size. GPower was used to estimate statistical power for the primary hypotheses. Assuming 8 couples (16 participants), with 4 couples in each group and two waves of data each, the statistical significance can be detected. Specifically, with power = .40, this study can detect an effect size of $f = .80$ (Using t-test statistics). Also chi-square test will be used to test the effectiveness of the intervention with power = .40. With this level of power, this study can detect an effect size of $f = .60$ (Using chi-square statistics).

The PI will continually monitor the study design to determine if there is a need to make modifications or discontinue the study due to lack of efficacy from therapeutic intervention.

Safety

Compensation for research related injury

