The therapy that participants are receiving is not experimental, rather the data collection procedures comprise the research. After 8 weeks of sessions, if participants request additional therapy, the PI will continue to be their therapist until their issue is resolved or they secure another therapist. The PI will also provide referral information in case participants would like to continue with another therapist.

Data and Safety Monitoring

Data Monitoring. The proposed research will include data from approximately 8 couples. The final dataset will include self-reported demographic and behavioral data, along with cortisol levels and heart rate information. All identifiers will be removed from the final dataset prior to release for sharing.

Data will be reviewed after every assessment session. The PI will analyze the data from the first cohort before proceeding with the next to determine if the research should proceed as planned, if PI needs to modify the protocol or discontinue the research (e.g., if Group 2 is doing better than Group 1).

Safety Monitoring. The PI will be responsible for monitoring the safety of the participants. In this study, the welfare of the participants will be of primary concern during treatment. There are a number of interventions cited in the literature for clinicians concerned about violence occurring between partners in between therapy sessions. Several prevention strategies and safety interventions from the literature will be used to prevent and deal with situations that may arise. These strategies and interventions are described in the attached Safety Chart.

Careful assessment will be conducted to understand the dynamics of situational couple violence and potential safety issues that couples are experiencing. The PI will ask questions about whether participants feel they are in danger. If participants are afraid that their partner will retaliate after disclosing sensitive information, these couples will be excluded from the study. Withdrawal from the study will be honored without any coercion.

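### Aim 2 tests change in graded outcomes with chi-square only, and the comparison with the randomised wait-list group is implied but never specified

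*Combined protocol and SAP*

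**What the plan says.** Under Study Design & Objectives, Aim 2 asks "whether the reported intensity of IPV for couples decreases after couples start therapy and whether this change is correlated with" HPA and PNS regulation. The Data analysis plan restates it: "The objective of this aim is to understand whether violence decreases over time following therapy", and whether physiological change goes with it. The method follows: "For this purpose, series of chi-square-test will be used as well as qualitative analysis". T-tests are assigned to Aim 1, on the pretest wave. Aim 3 is qualitative.

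On design, "Distribution of participants to the two groups will be randomized", four couples starting therapy at once and four after an 8-week wait (plus or minus 10 days). Group 2 is assessed before the wait, and "All the physiological and behavioral data collection will be repeated once Group 2 starts therapy". Data and Safety Monitoring calls the waiting couples a control group.

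A group comparison surfaces in two places. The power paragraph assumes 8 couples, "with 4 couples in each group and two waves of data each", gives power .40 for an effect of .80 with a t-test, and adds: "Also chi-square test will be used to test the effectiveness of the intervention", with power .40 for an effect of .60. Data and Safety Monitoring gives "if Group 2 is doing better than Group 1" as an example of a reason to modify or discontinue the research.

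**The concern.** There are two gaps.

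First, the test does not fit the question. The Screening Measures section describes the CTS2 as capturing how intense and how frequent conflict is, and cortisol and heart rate variability are continuous. A chi-square test needs categories, and no cut-off is given. It yields no correlation between graded changes. In its ordinary form it also ignores that the same couples are measured before and after.

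Second, change after therapy within treated couples has no comparator. A fall could reflect natural fluctuation, repeated assessment, or the stress and anger training given to all participants. It could also reflect regression to the mean, whose direction is unclear because entry requires some violence but excludes severe or frequent violence. The randomised wait addresses these explanations, but no analysis with a stated endpoint and time point uses it. An undefined group comparison could also feed a decision on whether the research continues.

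**Working it through.** The plan states neither alpha nor whether a continuity correction applies. Alpha .05 two-sided is assumed throughout, and chi-square is shown both ways.

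**1. The plan's own figures.** Chi-square power is P(χ²(1, λ) > 3.84) with λ = N·w². With w = .60 and N = 8 couples, λ = 2.88 and power is .396, which matches the stated .40. With N = 16 participants, λ = 5.76 and power is .670. The figure therefore treats the couple as the unit in a 2×2-type test, although the text also cites 16 participants. The t-test figure does not reproduce: reading .80 as d, power is .16 with 4 per group and .32 with 8 per group. Reading it as f (d = 1.6) gives .48 with 4 per group.

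**2. Information lost by dichotomising (within-couple change, 8 couples).** Assumed: normal scores, a fall of 0.8 SD, and pre-post correlation r. The standardised mean change is dz = 0.8/√(2(1−r)). The paired t-test has noncentrality dz·√8 on 7 df. The other rows enumerate all outcomes for 8 couples, with the cut-off chosen to favour each test.

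| | r = .3 | r = .5 | r = .7 |
|---|---|---|---|
| dz | .676 | .800 | 1.033 |
| Paired t, graded score | .38 | .50 | .71 |
| Chi-square, uncorrected | .28 | .26 | .24 |
| Chi-square, corrected | .12 | .10 | .08 |
| McNemar, uncorrected | .24 | .24 | .23 |
| McNemar, exact | .03 | .03 | .02 |

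**3. What ignoring the pairing does.** With no true change, and prevalences from .05 to .95, the largest size of the unpaired chi-square is 4.8%, 3.0% and 1.4% uncorrected (r = .3, .5, .7), and 1.0%, 0.5% and 0.2% corrected. All are below 5%, so the cost is power and not false positives.

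**4. The randomised contrast, 4 v 4 couples.**
- t-test, 6 df, d = .8 in SD of change: noncentrality .8·√(4/2) = 1.13, power .16.
- Exact permutation test: about .10 by simulation. There are C(8,4) = 70 allocations, so the smallest two-sided p is 2/70 = .029.
- Chi-square at its best cut-off: .18 uncorrected, .03 corrected or Fisher.
- Size of the uncorrected chi-square: at most 7.0% (prevalence .5). For example, 3/4 v 0/4 gives p = .028, against .143 by Fisher.
- 95% CI half-width: t(.975, 6)·√(1/4 + 1/4) = 2.447 × .707 = 1.73 SD of change.

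**5. Precision of the descriptive parts.** Mean within-couple change: t(.975, 7)/√8 = 2.365/2.828 = .84 SD of change. A change-score correlation of .5 in 8 people: Fisher z = .549 ± 1.96/√5, which gives −.32 to .89.

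**6. Shortest window.** The wait can be as short as 56 − 10 = 46 days. In Group 1, eight weekly sessions span at least 49 days from first to last, and the post-test can follow 7 − 5 = 2 days later, which makes 51 days.

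**The case against.** The strongest reply is that the section does name a test that fits. The power sentence with two groups and two waves cites a t-test. That cannot be Aim 1, which uses one wave, or Aim 3, which is qualitative, so Aim 2 is its natural home. This stands in part. It would be wrong to infer that a group comparison was never intended or that no test is named for one. What is missing is the endpoint, time point, unit and link to an aim, and the Aim 2 paragraph still names only chi-square.

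A reader might also infer that unpaired chi-square on paired data would produce false significance. Step 3 shows the opposite. Inflation appears only in the uncorrected 4 v 4 table, it is small, and the plan does not say that version would be used.

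Another tempting inference is that the one-year count in the exclusion criteria is also the outcome recall period, so that most of a post-test report would predate the randomised window. No passage applies that look-back to an outcome.

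The larger power loss in step 2 concerns uncontrolled change. In the randomised contrast the gain is modest: .16 or .10, against .18 for a test with size up to 7.0% and .03 for a valid one. Low, skewed violence counts are plausible, and they would weaken the normal-theory figures. Finally, this is declared a feasibility study with a qualitative component. That lowers the stakes, but the plan also says it will test effectiveness.

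**Conclusion.** The point holds as a should-fix. Aim 2's one named quantitative method does not suit its graded outcomes and cannot deliver the correlation the aim asks for. The randomised comparison is under-specified, not absent. For within-couple change the avoidable loss is from .38–.71 to .28–.24 at best, and to .12–.08 with a continuity correction. These figures rest on normal scores, a 0.8 SD fall, r from .3 to .7, and alpha .05 two-sided, none of which the plan states. The documents do not support a claim of inflated error from ignoring pairing. Nor does correcting the analysis make the study able to confirm an effect: with 4 v 4 couples it gives an estimate with a wide interval.

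**What to change.** In Aim 2, replace chi-square with couple-level change in the graded CTS2 score, and state the following.

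1. **Therapy effect.** Compare Group 1 pre to post with Group 2 start to end of wait. Report the difference with a 95% CI and an exact permutation p-value. Make this the only analysis that supports a statement about therapy. Fix one CTS2 recall period that fits within the shortest allowed window (46 days by step 6), and report the actual interval for each couple.
2. **Change over time.** Report within-couple pre-post and follow-up change with CIs, labelled uncontrolled and descriptive.
3. **Link to physiology.** Correlate change in CTS2 with change in each marker, men and women separately, with CIs.
4. **If violence is also dichotomised**, state the cut-off, recall period and unit. Use Fisher's exact test between groups and exact McNemar within couples, the latter descriptive because entry selects for violence.

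Tie the t-test power sentence to item 1, and use the same defined comparison where the monitoring text compares the groups.

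The cost is wording; no new visits are needed. The contents of the assessment schedule and flow chart were not available for this review, so the authors should confirm that the CTS2 is given at both Group 2 assessments and that the second precedes its first session, as the Study Design section suggests. The price is candour about precision: a half-width of about 1.7 SD of change for the main contrast.

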The main hypothesis of the proposed study is that conjoint therapy will gradually promote affect regulation of both partners in orchestration; i.e., improvement in one partners' ability to regulate emotions will have a positive effect in the other partner's ability to regulate emotions. If the outcome of this project supports this hypothesis, these results will provide biologically interpretable and quantitative grounds for the effectiveness of conjoint therapy and pave the way for more comprehensive and large scale effectiveness studies, which, in turn, may establish conjoint therapy as a strategy that will complement "parallel track" treatment in preventing and diminishing IPV.

The physiological processes that were found to link attachment and affect regulation include parasympathetic regulation of heart rate and Hypothalamic Pituitary Adrenal (HPA) axis activity (Beauchaine, 2001; Böhnke, Bertsch, Kruk, & Naumann, 2010; Porges, 2001). There is increasing evidence for the role of HPA axis in the development and enhancement of aggressive behavior in youth as well as adults. Furthermore, cardiac vagal tone, a common physiological marker of the regulation of the Parasympathetic Nervous System (PNS), is correlated with both anxious and disruptive behaviors (Böhnke, Bertsch, Kruk, & Naumann, 2010; Porges, 2001). Putting these observations together, the proposed research further hypothesizes that, through promotion of affect regulation, attachment based couple therapy will enhance regulation of PNS and HPA activity in couples, which in turn will have a diminishing effect on IPV.

In summary, the proposed research integrates research findings on the links between couple therapy, affect regulation, physiological markers of emotion regulation, and IPV to hypothesize and test a novel psychophysiological model for the mechanisms of change induced by couple therapy in the context of IPV.

Target Subject Population

Subject population:

Inclusion criteria:

- 1) This study is open to married, dating, and cohabiting couples.
- 2) Couples will have to be involved in an intimate relationship for at least one year with the current partner.
- 3) Both partners have to be older than 18 years of age at the time they signed the consent form.
- 4) Couples must have mild to moderate forms of situational couple violence.

Principal Investigator: [name]

Protocol Summary for IRB: Feasibility Study of Couple Therapy Treatment for Situational Couple Violence (IRB# 09-13-27)

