All therapy sessions will be videotaped. These records will not include any identifying information. Video recorders will be placed in such a way that the faces of the participants will not be visible in the recording. These records will help the PI understand the dynamics of the couples and identify potential adverse events. Audio records will not be sufficient for this purpose, since the participants' body language (their posture, the way they sit, their distance from each other) provides important information in this regard. Recorders will be located behind the participants, and only the back of their head will be visible. We will also make every effort to keep the videos in a safe and secure location. Recordings will be kept in a locked cabinet at the PI's office at the W.O. Walker Center, room 12-126 in the Mood Disorders Program on the 12th floor. The PI's office is locked and access is limited to only those individuals permitted access on the Walker ID badge. The video tapes will be destroyed after 2 years upon completion of the study. The building has a private security firm available 24 hours.

All therapies will be conducted as a couple. Training on stress management and safety planning will be performed as individuals. There will not be any group sessions. The goal of couple therapy is to help and improve couples' capacity to regulate emotions, solve problems, and communicate through therapy with the couple together. The specific steps that will be followed in conjoint/couple therapy are the following:

Principal Investigator: [name]

Protocol Summary for IRB: Feasibility Study of Couple Therapy Treatment for Situational Couple Violence (IRB# 09-13-27)

Week 1: Engagement

Goals:

The overall goal at the beginning of therapy is to create an alliance with both partners; that is, to create a relationship with each individual in which the therapist is warm, supportive, understanding, genuine, and empathic. In other words, both partners in the room will feel that the therapist understands their experience and is someone with whom they will be able to explore new behaviors and new ways of interacting with each other.

Interventions & Mechanisms:

Creation of alliance. The creation of alliance occurs through joining with each partner, then exploring each partner's experience of the problem.

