All participants in therapy appear more flexible in their relationship positions to one another. Responses are empathetic and emotionally receptive. Both partners monitor and regulate negative affect in an emotionally engaged manner. A sense of connectedness exists between both partners, as well as a decrease in negative cycles.

Principal Investigator: [name]

Protocol Summary for IRB: Feasibility Study of Couple Therapy Treatment for Situational Couple Violence (IRB# 09-13-27)

Data Collection

For each couple, data will be collected at each visit. Data will be collected in two forms:

1. Self-report and partner-report questionnaires will be collected using several measures, all of which have adequate reliability and validity.
2. Physiological data will be collected by monitoring heart rate variability and cortisol level at the DCRU.

Screening Measures

In order to examine eligibility, demographics and some clinical data will be collected.

- CAGE questionnaire. CAGE is a brief alcoholism screening test (Mayfield D, McLeod G, Hall P.1974)
- Simple Screening Instrument for Substance (SSI-SA). Abuse (SSI-SA) The SSI-SA was intended as a brief screen of substance abuse symptoms. It was designed utilizing a binary (yes/no) response format to facilitate scoring and to minimize subjective interpretation of scores Center for Substance Abuse Treatment. (1994).
- Conflict Tactics Scale 2 (CTS2;Straus, Hamby, BoneyMcCoy, & Sugarman, 1996) assesses intimate partner violence based on partners' rating of their own and their spouse's conflict strategies, measuring the intensity and frequency of psychological/verbal and physical conflict. This scale has been shown to have good reliability and validity (Straus, Hamby, BoneyMcCoy, & Sugarman, 1996). This is also be used throughout the study to monitor couple's relationship change.
- Symptom Checklist (SCL90-R) (Derogatis, 1994) will be used to assess acute psychopathology. This measure will also be used throughout the study to monitor participants' mental health change.

Outcome Measures

Both behavioral and physiological measurements will be used to evaluate the effectiveness of conjoint therapy. No medical records will be reviewed at any time.

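### Aim 3 carries the main hypothesis, but the only method named for it is grounded theory, which cannot estimate the lagged partner-to-partner links or the effect on IPV

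*Combined protocol and SAP*

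**What the plan says.** Under Hypotheses: "The main hypothesis of the proposed study is that conjoint therapy will gradually promote affect regulation of both partners in orchestration". The sentence goes on to explain that improvement in one partner's "ability to regulate emotions will have a positive effect in the other" partner's. If the results support this, they are to give "biologically interpretable and quantitative grounds for the effectiveness of conjoint therapy".

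Under Study Design & Objectives, Aim 3 is: "Examine the longitudinal effects of partners' psychophysiological regulation on each other's psychophysiological regulation and on IPV".

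Under Efficacy & Data Analysis, Data analysis plan, the Aim 3 entry has two parts. It says that "links from emotion regulation of each partner to the emotion regulation of the other partner at the next time point are included", without saying in what model. It then gives the method: "Qualitative analysis with a grounded theory approach will be used". IPV does not appear in that entry.

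**The concern.** The Aim 3 variables are numeric: salivary cortisol, vagal measures and questionnaire scores. Grounded theory builds concepts from qualitative material. It gives no coefficient or interval for the link from one partner's physiology to the other's at the next assessment, or from physiology to IPV. Followed exactly, the plan therefore has no defined quantitative answer to its own main hypothesis, although quantitative evidence is the contribution the protocol claims over earlier, mostly self-report work.

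If a lagged analysis is run anyway, several choices remain free after the data are in. The results are meant to prepare larger effectiveness studies, so a link found by such a choice could be carried forward as a finding.

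**Working it through.** The plan gives no sample size, power or effect size for Aim 3, so there is no figure to reproduce. The check is textual, followed by arithmetic on what a repair could show.

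**1. Does another part of the document supply the estimate?**

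| Method named | Where | Assigned to | Estimates a lagged partner link? |
|---|---|---|---|
| t-tests | Data analysis plan | Aim 1, cross-sectional at pre-test | No |
| Chi-square tests, qualitative analysis | Data analysis plan | Aim 2, change after therapy | No |
| Power statement for the primary hypotheses | Data analysis plan | A t-test and a chi-square test only | No |
| Confirmatory factor analysis | Behavioral Measures | Combining questionnaires | No |
| Grounded theory | Data analysis plan | Aim 3 | No |

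Quantitative methods assigned to Aim 3 in the readable text: 0.

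**2. Is the qualitative source named?** No readable text links any qualitative material to Aim 3. Session video is a possible source, but its stated use is different: "These records will help the PI understand the dynamics of the couples and identify potential adverse events".

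**3. What is fixed and what is open?** The Aim 3 entry fixes the direction (each partner to the other, so both ways) and the lag (the next time point). It leaves open:
- the marker: Physiological Measures plans a baseline and three post-task saliva collections, and both vagal tone and vagal reactivity;
- the model form;
- which wave pairs count.

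**4. How many lagged intervals are there?** Physiology is planned at pre-test, post-test and follow-up. That gives 2 intervals with 8 couples each. Group 2 is also measured before its wait, which adds 1 interval with 4 couples. With no dropout, the couple-level transitions are 8 × 2 + 4 × 1 = 20. Study Design also plans a few assessments at every therapy session, and Behavioral Measures lists affect regulation among the questionnaires for each visit, so self-report may add time points. Table 2 could not be read, so this is unsettled.

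**5. What could 8 couples show?** Take one interval, one marker and one direction. Regress one partner's later value on both partners' earlier values: 8 rows, 3 parameters, 5 df.
- Interval for a partial r of .3 (Fisher z, one covariate): SE = 1/√(8 − 3 − 1) = .5; atanh(.3) = .310; .310 ± 1.96 × .5 = −.670 to 1.290; back-transformed, −.59 to .86.
- Smallest |partial r| that excludes zero: t/√(t² + 5) with t = 2.571 gives .754.
- Simulated power at partial r of .3, .5 and .7: about .10, .21 and .46.

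**6. How often would chance mislead?** Simulation with no partner effect: value = couple + person + occasion, total variance 1. Assumed ranges: person share .2 to .5, couple share 0 to .5 (some occasion variance must remain, so not both at the maximum), and correlation between the partners' occasion components 0 to .3.
- Each lagged coefficient excludes zero in 4.9% to 7.8% of runs.
- The highest rate came at person share .2, couple share .5, occasion correlation 0. There the correlation is .7 with one's own earlier value, .5 with the partner's earlier value, and .5 between partners at one time. The population partial r is (.5 − .7 × .5)/√[(1 − .49)(1 − .25)] = .24, and the simulated mean was .22. Stable couple similarity alone produces it.
- At least one of 8 coefficients (2 markers × 2 intervals × 2 directions) excludes zero in 33% to 48% of runs, taking the markers as independent. As a rough check, 1 − (1 − .049)⁸ = .33 and 1 − (1 − .078)⁸ = .48.
- Between-partner correlation of change: the stable couple and person parts cancel in a change score, so only the occasion components matter. The simulated mean was about 0, .14 and .28 when those components correlate 0, .15 and .3. In the setting above, the total same-time correlation is .50 and the change correlation is about 0.

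**The case against.** The strongest defence is that the study calls itself a feasibility study gathering pilot data and that Aim 3 is worded as exploring patterns. A qualitative strand is legitimate in such a study. That stands, and it limits the seriousness of the point. It does not remove the mismatch, because the same aim speaks of change in one partner as a function of the other's physiology, and the Hypotheses section promises quantitative grounds and a test of a model.

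A second defence is that 8 couples cannot support a lagged model. They cannot support a confirmatory one. Eight small regressions are a debatable choice even for description, since plots and simple summaries would serve a feasibility aim with less risk of misreading. That also stands, so the regressions should be optional.

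Three stronger readings are tempting, and the documents do not support them:
- A reader might infer that everything about a lagged analysis is open. The plan fixes both directions and the next-time-point lag.
- A reader might infer that Aim 3 has only two lags. That is shown for physiology only; session-level self-report may add more.
- A reader might infer that no method exists anywhere because none is visible. Fig 1 and the body of Table 2 are missing from the text. They are labelled a flow chart and an assessment schedule, and nothing suggests that they hold an analysis method, but they could not be read.

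**Conclusion.** The point holds as a mismatch between aim and method and should be corrected before analysis. It does not undermine the feasibility purpose. The conclusion rests on the wording alone and not on any simulated figure.

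The figures bear on the repair. They assume no dropout, the stated variance shares and independent markers. They show that any quantitative Aim 3 analysis here can generate hypotheses but cannot confirm one, and that no single interval should be read as support. Correlated change between partners is not evidence of partner influence either: a shared occasion, such as the joint conflict discussion, can produce it.

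**What to change.** In the Aim 3 entry of the Data analysis plan, specify an exploratory, descriptive quantitative analysis with the couple as the independent unit:

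1. Name in advance one HPA marker, one PNS marker and one CTS2 score, and state the wave pairs. The CTS2 is already repeated: "This is also be used throughout the study to monitor couple's relationship change".
2. Plot every couple across waves for each marker. Show the Group 2 wait (4 couples) as plots only.
3. Report the between-partner correlation of pre-to-post change as descriptive only, with the shared-occasion caveat. For Group 2, use the pre-test taken after the wait.
4. For IPV, plot each partner's marker change against CTS2 change, or state that this limb is not analysed.
5. State whether self-reported regulation (DERS, CISS, per-session measures) belongs to Aim 3.
6. Treat lagged regressions as optional. If they are run, report all 8 coefficients with t-based 95% intervals.
7. Keep grounded theory as a separate objective with its source material named, and label all Aim 3 results hypothesis-generating.

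The smaller alternative is to reword Aim 3 in the objectives and the Hypotheses section so that the aim is qualitative only, its source is named, and quantitative grounds are no longer promised for the partner-to-partner hypothesis.

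The cost is analysis-plan wording and a little analysis time on data already planned, with no new visits or samples. The drawbacks are very wide intervals and the fact that 4 waiting couples cannot separate therapy from time.
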